Lung Cancer Surgery: Decisions Against Life Saving Care - The Intervention

NCT01687738

Protocol Date: May 13, 2011

Most Recent IRB Approval Date: March 29, 2016

Lung Cancer Surgery: Decisions Against Life Saving Care - The Intervention

STATISTICAL ANALYSES

Outcome Measures

Primary Outcome. Whether or not patients undergo lung resection surgery represents the main study outcome. We will conform to the 4 month standard used in the SEER database. To ascertain the result, we will first call patients' physicians to determine whether surgery occurred within the designated time frame. Given the possibility that individual patients could seek other opinions and receive surgical care elsewhere, when appropriate, we will ask the patient, or a family member (if the patient is dead or unavailable), whether surgery was performed by someone other than the index physician. If surgery has not occurred, we will ask for reasons. Through appropriate consent, we will retain the option of confirmatory medical records review. For secondary analyses, we will record surgeries that occur beyond the 4 month threshold.

Secondary Outcomes.

1. One year, post-enrollment survival in surgical and non-surgical groups
2. Satisfaction of patients that received interventions compared to those who did not
3. Patients' perceptions of communication for those patients that received intervention compared to those who did not
4. SF-12 scores at baseline, 6 months post-enrollment and 12 months post enrollment

6. Data Analysis:

Our current plan includes:

Descriptive statistics (means, standard deviations, frequencies, proportions, correlations, and graphical displays) will be computed for all study variables at baseline and post-baseline. The distribution of all outcome variables will be assessed to determine if distributional assumptions are valid. Descriptive statistics will be obtained for all the variables overall and by race and site. Statistical methods for addressing each of the specific aims of the study are detailed in this section. Since several statistical tests are planned, there is the possibility of incurring spurious results if we do not correct for multiple comparisons. All tests are based on a 2-sided alpha of 0.05.

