
hypothesis 1b. the communication intervention will be more effective in patients who score lower in measures of health literacy

Using the logistic regression analyses for clustered data as noted above, the interaction effects of health literacy, S-TOFHLA scores, and intervention group will be tested in all models. . S-TOFHLA scores will be tested as a continuous variable and also, separately, as a dichotomous variable comparing those categorized as inadequate or marginal literacy with those categorized as adequate literacy [103]. Cumulative pre-intervention surgical rates will be compared at all sites with post-intervention rates using Pearson's chi-square test. Post-intervention rates will be compared using test of proportions and changes in proportions from baseline will be compared between surgical and nonsurgical groups using appropriate methods. To determine if the post-intervention rate approaches maximal surgical rates, we will identify patients with high risk co-morbidities, above the age of 80, and need for pneumonectomy or multiple lobectomy in the "no surgery group", subtract this sum from the denominator then re-calculate the surgical rate. We will analyze the secondary specific aim, To measure the effect of the intervention on patients' perceptions of communication and satisfaction with care, by dichotomizing these variables and replacing surgery as the dependent variable in chi-square and logistic regression models as described under the specific aim above.

Specific Aim 2. To reduce the documented difference in lung resection surgery and mortality between African-American and White patients with early stage, non-small cell

lung cancer.

hypothesis 2a. giving physicians who make lung cancer surgery decisions data relating co-morbidity to surgical outcomes will reduce racial differences in surgery

hypothesis 2b. using a real time lung cancer registry to provide physicians race-specific feedback about their surgical treatment of early stage lung cancer patients will reduce racial differences in surgery

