We will analyze patient level cross-sectional dichotomous outcome data using logistic regression growth models. We will both limit analyses to the cancer communicator control group and do an all enrollee analysis by adding a communicator intervention / no communicator intervention predictor variable to the models. First, we will fit a saturated growth model to estimate annual proportions of these outcomes, before and after the registry/feedback intervention, to assess the effects of the intervention on these outcomes by contrasting the proportions before and after the interventions. We will test the null hypothesis that the proportions before and after the intervention are the same. We will repeat this analysis by including "race" and "race x time" interaction in this model to examine changes in these outcomes between the two races and also if there are any differential changes over time. We will test the null hypothesis that the proportions before and after the intervention are the same for each race

Data interpretation: If our data feedback / registry intervention is found to produce an effect in less than the 4 Cancer Centers, it will prompt further examination of the factors that moderate or mediate the relationship between the intervention and completion of cancer treatment. Thus, by conducting an embedded randomized cohort-control study of the Cancer Communicator intervention component, we may be better able to provide more information about the dimensions along which these interventions can or cannot be generalized.

hypothesis 2c. a cancer communicator who utilizes active listening and teach-back methods during discussions about lung cancer surgery with newly diagnosed, early stage patients will increase the rate of surgery in African-American patients more than Caucasian patients compared to usual care.

We will compare post intervention, unadjusted, surgical rates between African-American and White lung cancer patients using chi-square analysis as discussed under Aim 1. We will also perform the maximum rate analysis stratified by race. The regression models described above under Aim 1. We will also apply these analyses to patients in the communicator group alone selecting patients on an intention to treat basis.

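### Hypotheses 2a and 2b claim a narrower racial gap, but the stated race-specific null is no change within each race; the race-by-time term that addresses the gap is not named as the test

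*SAP*

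**What the plan says.** Under Specific Aim 2 (SAP, section 6, Data Analysis), hypothesis 2a is that "data relating co-morbidity to surgical outcomes will reduce racial differences in surgery". Hypothesis 2b says the same of the registry: "race-specific feedback about their surgical treatment of early stage lung cancer patients will reduce racial differences in surgery". Both are statements about a change in the Black-White difference.

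The analysis paragraph for 2a and 2b specifies logistic growth models. It states two nulls. The first is that the overall proportions before and after the registry and feedback are equal. The second, after race and race by time enter the model, is: "We will test the null hypothesis that the proportions before and after the intervention are the same for each race". The purpose given for the added terms is "to examine changes in these outcomes between the two races and also if there are any differential changes over time". Two analysis sets are planned: "We will both limit analyses to the cancer communicator control group and do an all enrollee analysis". The general rule is "All tests are based on a 2-sided alpha of 0.05".

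Section 6 also provides for interim analyses of Aims 1 and 2. The study stops early if significant benefits are shown both on surgical rates and on narrowing of disparities. No test is named for the second part. Section 7 gives race-specific power only for a rise within each race.

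**The concern.** A null of no before/after change within a race concerns that race's own rate. It is false when both races improve equally, and also when White patients improve more than Black patients. Rejecting it is therefore compatible with a gap that is unchanged or wider, whereas 2a and 2b assert a gap that is narrower.

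The race-by-time term does bear on the question, but the SAP gives it no null, no direction and no scale. Under hypothesis 1b, by contrast, the SAP says outright that the literacy-by-intervention interaction will be tested. A reader of the Aim 2 results would not know which result answers 2a and 2b, and a committee applying the termination condition would not know which result to look at.

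**Working it through.** **Inputs**
- Starting rates of 0.55 (Black) and 0.66 (White), a gap of 11 points: SAP section 7.
- After-period patients, 159 Black and 337 White: SAP section 7.
- Before-period charts: Protocol section D expects 100 to 150 per site, so 400 to 600 over four sites. Two years of the 2007 registry table (Protocol section C) would give 2 × 327 = 654.
- Black share of the charts is not given for this sample. The 2007 table has 66/327 = 20%. I assume 20 to 30% for 400 to 600 charts, and 132/522 for the 654 case, counting all other cases as White.
- Clustering is ignored; section 7 reports correlations of −0.002 to 0.01.

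**The plan's own figures.** One-sample test, two-sided 0.05: power = Φ{[√n(p1 − p0) − 1.96√(p0q0)] / √(p1q1)}.
- All, n = 496, 0.63 to 0.69: 80.0%.
- Black, n = 159, 0.55 to 0.66: 80.8%.
- White, n = 337, 0.66 to 0.73: 78.9%.

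These reproduce the stated 80%, and all three concern a rise within a group. No power is given for a change in the gap.

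**Gap unchanged: both races rise 10 points** (0.55 to 0.65; 0.66 to 0.76). Per-race two-sample test: power = Φ[(d − 1.96·SE0)/SE1], with SE0 pooled and SE1 unpooled. For 400 charts, 20% Black (80/320):
- Black: SE0 = 0.0666, SE1 = 0.0673; Φ[(0.10 − 0.1306)/0.0673] = 0.324.
- White: SE0 = 0.0354, SE1 = 0.0352; Φ[(0.10 − 0.0693)/0.0352] = 0.808.
- Both reject: 0.324 × 0.808 = 0.262. At least one: 1 − 0.676 × 0.192 = 0.870.

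| Charts (Black/White) | Black rejects | White rejects | Both | At least one |
|---|---|---|---|---|
| 400 (80/320) | 32% | 81% | 26% | 87% |
| 600 (180/420) | 47% | 85% | 40% | 92% |
| 654 (132/522) | 41% | 88% | 36% | 93% |

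A direct test of the change in the gap rejects at its nominal 5%. In the usual-care group alone (1:1 allocation assumed, 80/168 after), both reject in about 16 to 21%.

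**Gap widens to 16 points** (Black 0.55 to 0.60, White 0.66 to 0.76). By simulation (200,000 runs per case), both per-race nulls are rejected in about 10 to 13% of trials with all enrollees.

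**Scale.** The equal 10-point rise leaves the rate gap at 11, but the log-odds rise by 0.42 in Black and 0.49 in White patients, so the logit interaction is not zero. Conversely, an odds ratio of 1.5 in both races gives zero interaction, yet the rates become 0.647 and 0.744 and the gap 9.7 points.

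**Power of the direct test.** SE² is the sum of p(1 − p)/n over the four race-by-period cells. For an illustrative narrowing of 4 points (0.55 to 0.66; 0.66 to 0.73), SE is 0.0761 with 80/320 charts and 0.0625 with 180/420. Power is Φ(0.04/SE − 1.96) + Φ(−0.04/SE − 1.96), or 8.2% and 9.8%. The change detectable with 80% power is 2.80 × SE, about 17.5 to 21 points, more than the whole 11-point gap. Complete closure (Black 0.55 to 0.66, White flat) has about 30 to 41% power.

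**The case against.** The strongest reply is that the right contrast is already planned. Race by time is the change in the gap on the log-odds scale, it sits in the same model, and the general two-sided 0.05 rule could be taken to cover it. This stands to the extent that a reader who infers that the plan has no analysis of the gap would be wrong. It does not supply what is missing: the term is not named as the test of 2a and 2b, and no scale is set.

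A reader might also infer that Aim 2 would be declared positive, or the trial stopped, once a per-race null is rejected. The documents do not say so. They give no success rule for 2a and 2b, and on its face the termination condition would not be met by an unchanged or wider gap. The defect there is an unspecified test.

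The figures of about 90% come from counting a rejection in at least one race, and the White test drives them. A significant rise in White patients alone would hardly be reported as a smaller disparity. Since the null is worded for each race, requiring both is at least as natural, and 26 to 40% is the fairer figure.

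On scale, the hypotheses name none and the growth model already yields proportions, so the rate gap can be obtained. The scale needs only to be stated.

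**Conclusion.** The stated race-specific null does not answer hypotheses 2a and 2b, and the term that does is left without a designated role. With the gap unchanged at 11 points, both per-race nulls are rejected in about 26 to 40% of trials and at least one in about 87 to 93%, against 5% for a direct test. If the gap widens to 16 points, both are still rejected in about 10 to 13%.

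These figures rest on assumptions the documents do not settle: the number of charts, their Black share, before-period rates equal to those of the previous study, and no clustering effect. The mismatch itself rests on none of them.

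Section 7 should not be read as predicting a narrowing from 11 to 7 points. Its race-specific figures are detectable increases computed separately from fixed sample sizes, and the 4-point change is used here only as an illustration. Aim 2 is not the primary comparison, so this is a correction that should be made rather than a flaw in the trial's main result.

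**What to change.** In the Aim 2 analysis paragraph, replace the final null with this: for 2a and 2b, the Black-White difference in the proportion having surgery is the same before and after the registry and feedback. Name the race-by-period contrast as its test, two-sided at 0.05, with narrowing as the hypothesised direction. Report the change in the gap as a difference in proportions with a 95% CI from the fitted model, in both analysis sets already planned. Because the growth model estimates annual proportions, state how years are combined into before and after. Keep the per-race before/after comparisons as supportive. In the interim paragraph, state that the disparities condition refers to this contrast.

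The cost is SAP wording only; no new data or model is needed. The drawback is low power: about 8 to 10% for a 4-point narrowing with all enrollees, and about 7 to 8% in the usual-care group under 1:1 allocation. The SAP should say so, let the estimate and interval lead, and warn that a non-significant result is not evidence of no change.

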The main outcome of interest is whether patients undergo surgery is a dichotomous variable, either yes or no. We will compute proportions to estimate the probability of surgery for blacks and whites and compute 95% confidence intervals for the proportions. Since the main outcome is dichotomous, logistic regression for clustered data (clustered within sites) using multiple predictors will be used to assess the simultaneous effect of predictors on the outcome.

Specific Aim 1. To maximize surgical rates for all patients with stage I and II, non-small cell lung cancer who do not have absolute contraindications for lung resection surgery.

hypothesis 1a. a cancer communicator who utilizes active listening and teach-back methods during discussions about lung cancer surgery with newly diagnosed, early stage patients will increase the rate of surgery in Caucasian and African-American patients who do not suffer absolute contra-indications for lung cancer surgery compared to usual care

The primary outcome variable, surgery yes or no, will be compared in the control group randomized to usual care, to the intervention group randomized to the cancer communicator. Bivariate analyses will be performed using the surgical outcome as the dependent variable. Independent variables in these analyses will include important group, demographic variables

such as age, race, marital status, household income, health insurance, gender, and education as well as measures of trust, patient satisfaction, functional status, self-reported health, comorbid illness, perceptions of communication, and the communication intervention. We will use bivariate analyses, including correlations and chi-square tests of association, to make preliminary assessments of the relationships between study variables, overall and by race.

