The modeling approach will be to initially define as large a maximum model as possible using main effects only (initially no interactions). Preliminary analyses of similar data indicates that the sample size combined with a sufficient number of events (surgery yes) will allow upwards of 30-35 main effects to be included in the model with good reliability for estimation and inference. The generalized estimating equations (GEE) for binary outcomes will be used to fit logistic regression models for clustered data [102]. The primary outcome variable is binary, surgery yes or no, and outcomes of patients clustered within the same site (and/or MD) are expected to be correlated. GEE will allow fitting a logistic regression to the binary outcome while adjusting for the effect of clustering within the same site (and/or MD). As stated previously, independent variables in these analyses will include important demographic variables such as age, race, marital status, household income, health insurance, gender, and education as well as measures of trust, patient satisfaction, functional status, self-reported health, comorbid illness, perceptions of communication, and the communication intervention. The significance of each of the main effects while adjusting for all other effects from the maximum model will be assessed. A backwards elimination approach will, initially, remove effects with a p-value of greater than 0.10. This excludes selected predictors forced predictors into the model (forced predictors include group, comorbid illnesses and selected baseline scores). The reduced model will be refit. Variables have p-values greater than 0.05 will then be removed. The final reduced main effects model, including forced predictors will be refit. Selected interactions will be considered for inclusion into the final reduced main effects model. For the secondary outcomes, survival analysis techniques will be used to assess the one year, post-enrollment survival in surgical and non-surgical groups. Kaplan-Meier curves will be generated. Linear regression models for repeated measures (discrete) outcomes using GEE will be used to assess patient satisfaction of patients that received interventions compared to those who did not, for patients' perceptions of communication for those patients that received intervention compared to those who did not, and for SF12 scores at 6 months post-enrollment and 12 months post enrollment. Covariates will include baseline, group, and other covariates listed above.

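### Hypothesis 2c concerns a race-by-arm difference in the communicator's effect, but the tests named for it measure the remaining Black–White gap in surgery

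*SAP*

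**What the plan says.** Under Specific Aim 2, hypothesis 2c says that the communicator "will increase the rate of surgery in African-American patients more than Caucasian patients compared to usual care". Four analyses follow in the same section.

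- A race comparison: "We will compare post intervention, unadjusted, surgical rates between African-American and White lung cancer patients using chi-square analysis". The sentence goes on to refer to the discussion under Aim 1.
- "We will also perform the maximum rate analysis stratified by race".
- A sentence without a verb: "The regression models described above under Aim 1".
- A repeat restricted to one randomised arm: "We will also apply these analyses to patients in the communicator group alone selecting patients on an intention to treat basis".

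Two parts of Specific Aim 1 bear on the cross-references. The bivariate work there uses correlations and chi-square tests "to make preliminary assessments of the relationships between study variables, overall and by race". The GEE logistic models start from main effects with no interactions and then go through backward elimination. The "forced predictors include group, comorbid illnesses and selected baseline scores"; race is not in that list. After elimination, "Selected interactions will be considered for inclusion into the final reduced main effects model".

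Elsewhere the SAP does name its interactions: health literacy by intervention group for 1b, race by time for 2a and 2b, and race by clinical characteristic for Aim 3. Race by communicator arm is named nowhere. Section 7 gives no power for 2c.

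**The concern.** Testing 2c requires all four race-by-arm cells, because the quantity is (communicator minus usual care in Black patients) minus (communicator minus usual care in White patients). A Black v White comparison of post-intervention rates measures how large the racial gap is. In the communicator group alone, the usual-care comparator that 2c names is absent.

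A gap that existed before the trial and was left untouched by the communicator can make this test significant. A communicator that closed the gap would make it non-significant. The result therefore does not follow the truth of 2c.

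This matters beyond reporting. The interim-analysis paragraph at the end of section 6 covers Aims 1 and 2, and allows termination on significant benefit in surgical rates and in reduction of disparities. Hypothesis 2c belongs to Aim 2.

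**Working it through.** **Inputs.** From SAP section 7: 159 Black and 337 White patients, with prior surgery rates of 0.55 and 0.66. From section 6: two-sided alpha of 0.05. Assumptions: 1:1 allocation, giving 79.5 Black and 168.5 White patients per arm (the documents give no ratio), and the arm-specific rates below, which the documents do not give either. I build most of these from the increases in section 7 (+11 points for Black patients, +7 for White patients).

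**The plan's own figures.** One-sample test, power = Φ[(p1 − p0 − 1.96·√(p0(1−p0)/n)) / √(p1(1−p1)/n)]:

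- n = 496, 0.63 to 0.69: 0.800
- n = 159, 0.55 to 0.66: 0.808
- n = 337, 0.66 to 0.73: 0.789

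The stated 80% is reproduced, but it is for comparisons with the previous study and says nothing about 2c.

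**Black v White chi-square.** Power = Φ[(|d| − 1.96·s0)/s1], plus the small opposite tail. Here d is the difference in rates, s0 the standard error under a common rate and s1 the standard error under the two separate rates.

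With no communicator effect, d = 0.11 and the common rate is (159×0.55 + 337×0.66)/496 = 0.625.

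- All enrollees: s0 = 0.0466, s1 = 0.0471, so (0.11 − 0.0913)/0.0471 = 0.40 and power is 65%.
- Communicator arm: s0 = 0.0659, s1 = 0.0667, so (0.11 − 0.1292)/0.0667 = −0.29 and power is 39%.

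| Assumed communicator effect | Is 2c true? | All enrollees significant | Communicator arm significant |
|---|---|---|---|
| None in either race | No | 65% | 39% |
| +7 points in both | No | 67% | 42% |
| Black 0, White +7 | No, reversed | 88% | 80% |
| Black +11, White 0 | Yes | 22% | 5% |

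With one-third to two-thirds of patients in the communicator arm, the 39% becomes 28% to 49%. The 65% does not depend on allocation, because the rates are then the same in both arms.

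**The contrast that 2c describes.** The standard error of the difference of risk differences is √Σ p(1−p)/n over the four cells. For Black +11, White 0:

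√(0.2475/79.5 + 0.2244/79.5 + 2×0.2244/168.5) = √0.00860 = 0.093.

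This is about 9 points, so the 95% CI is about ±18 points. Power of the interaction test:

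| Assumed effects | Risk-difference scale | Log-odds scale |
|---|---|---|
| Black +11, White +7 | 0.04/0.092: 7% | 0.131/0.404: 6% |
| Black +11, White 0 | 0.11/0.093: 22% | 0.463/0.400: 21% |
| Both reach 0.72 (assumed) | 0.11/0.090: 23% | 0.463/0.411: 20% |

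For 80% power the Black effect must exceed the White effect by about 24–25 points. To detect +11 v 0, the trial would need about 496 × (2.80/1.187)² ≈ 2,770 patients on the risk-difference scale.

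**The case against.** The strongest defence is the cross-reference. The chi-square is to be done as discussed under Aim 1, and Aim 1 compares the communicator with usual care, with chi-square tests overall and by race. On that reading 2c includes arm comparisons within each race. A reader might infer that the plan for 2c contains no usual-care contrast at all, or that the first chi-square is expressly pooled over arms. The text supports neither: pooling is the natural reading, given that the communicator group alone is a separate step, but it is not stated. The defence still falls short, because Aim 1 calls those tests preliminary and two separate within-race tests do not test whether the effects differ.

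Second, the Aim 1 models could take a race-by-group term among the selected interactions. The test is therefore unspecified rather than excluded. That stands, but a term that may be considered after elimination, in a model from which race itself may have been dropped, is not a prespecified test of 2c. The verbless sentence may be a fault of text extraction, and I do not count it as a defect.

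Third, a reader might infer that the all-enrollee test has 65% power whatever the communicator does. It does not. If both races reach an assumed 0.72 in the communicator arm, the overall rates are 0.635 and 0.69, and the test is significant about 23% of the time.

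Fourth, nothing in the SAP says that a non-significant result in the communicator arm will be taken to mean that the gap has closed. That misreading is a risk, not a stated intention.

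Finally, section 7 names Aim 1 as the primary aim, and the right test has low power. The correction makes the inference valid; it does not make 2c answerable with precision.

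**Conclusion.** The point holds. As written, the tests named for 2c measure the residual racial gap and not the difference in the communicator's effect, and no cross-reference supplies a prespecified race-by-arm test. Across the assumed scenarios the Black v White test is significant more often when 2c is false (65–88% in all enrollees, 39–80% in the communicator arm) than when Black patients gain 11 points and White patients none (about 22% and 5%).

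These percentages rest on 1:1 allocation and on assumed arm-specific rates, and they move with both. The mismatch between hypothesis and test does not depend on them. The documents do not support the stronger claim that 2c could not be tested under this plan: the data and the model framework are there, and the term is missing.

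Given the termination provision for Aims 1 and 2, a Black v White chi-square should not be taken as evidence that the communicator reduced the disparity.

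**What to change.** Amend the text under hypothesis 2c as follows.

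1. Name the race-by-randomised-group term in the Aim 1 GEE logistic model as the test of 2c. Force race and group into the model and analyse all patients as randomised. This fixes the test on the log-odds scale. The scale must be stated because equal additive gains are not equal there: +7 points in both races gives a log-odds interaction of −0.04.
2. Report the communicator minus usual-care difference in surgical rate within each race, and the difference between the two with a 95% CI, on the risk-difference scale.
3. Label the Black v White chi-squares, in all enrollees and in the communicator group alone, as descriptive.
4. Complete or delete the unfinished sentence on the regression models.
5. State that 2c will be estimated with low power: a standard error of about 9 points, power of about 6–7% for +11 v +7 points, and about 20–23% for +11 v 0 or for full closure at an assumed 0.72. Restate these figures for the actual allocation ratio.
6. In the interim-analysis paragraph, say that the descriptive chi-squares are not evidence of a communicator effect on the disparity.

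The cost is SAP wording only, with no new data or patients. The downside is that the stated ability to answer 2c becomes less favourable.
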